2.2 Secondary estimands

Not applicable.

3 Study design

This is a three-cohort, multicenter prospective study in up to 66 participants with relapsing multiple sclerosis. Up to 44 of the participants will begin treatment with ofatumumab or already be on commercial ofatumumab, the remaining 22 participants will remain on their iDMT. In this study, participants must receive the 2020-2021, 2021-2022, or 2022-2023 inactivated influenza vaccine. Participants also must meet inclusion criteria and not meet exclusion criteria.

There are 3 study periods:

1. Screening Period:

Participants will enter a Screening Period of up to 1 week to assess eligibility requirements. Participants in Cohort 1 without Hepatitis B virus (HBV) and serum immunoglobulin results within the past 6 months prior to screening will require central labs drawn. Participants with Hepatitis B virus (HBV) and serum immunoglobulin results within the past 6 months prior to screening will not require the labs to be drawn.

2. Investigational Period:

All participants should receive an inactivated influenza vaccine within 9 calendar days after the Screening Visit, before the Week 0 Visit occurs. Participants will obtain the quadrivalent influenza vaccine at no cost to them from their local pharmacy using a pharmacy card supplied by Novartis or from the investigational site supply. Patients should be instructed to provide pharmacy documentation of vaccine administration to the Study Doctor at the next scheduled on-site study visit.

Participants in Cohort 1: Loading doses of 20 mg sc of atumumab will be administered at Week 2, 3 and 4.

Participants in Cohort 2: Will continue taking their prescribed of atumumab as per their dosing schedule throughout the Investigational Period.

Participants in Cohort 3: Will continue administration of their prescribed iDMT as per their dosing schedule in the Investigational Period.

3. Optional, 6-month open-label Extension Period:

The optional, 6-month open-label extension is designed to continue to observe the immune response.

Participants in Cohort 1 will administer their first dose of ofatumumab in the open-label Extension Period at Week 6. Thereinafter, they will continue monthly dosing until the final dose at Week 26. Novartis will supply ofatumumab to participants in Cohort 1 for the Extension Period.

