6.7.2 Instruction for prescribing and taking study treatment

All investigational medication will be provided by Novartis. Of atumumab treatment should be administered after study assessments have been completed for the visit.

Influenza Vaccine

The quadrivalent vaccine should be obtained at the patient's preferred pharmacy using the Novartis supplied pharmacy card or will receive the vaccine from the investigational site supply within 9 days of the screening visit.

Ofatumumab

Site staff should remove the study treatment from the refrigerator and allow the auto injector pen to reach room temperature in their unopened box (approximately 15-30 minutes) before self-injection by the participant. Used syringes should be disposed of immediately after use in a sharps container.

A different body site (front of thighs, lower abdomen) should be chosen each time a dose is administered to reduce the risk of an injection-site reaction; investigator/qualified site staff/caregiver can also inject the study treatment in the outer upper arms. Each new injection should be given at least one inch from the previously used site. If administration is in the abdomen, the 2-inch area around navel should be avoided. Study treatment should also not be injected into areas where the skin is tender, bruised, red, or hard, or where the participant has scars or stretch marks.

Participants in Cohort 1

The patients in Cohort 1 will receive their first loading dose of ofatumumab at the study site at Week 2 (2 weeks after receiving the influenza vaccine). The next loading dose of study drug will be dispensed to the participant at this visit to take home for administration at Week 3. The Week 4 dose will be administered in the clinic after the post-vaccine titer is drawn. Doses at Week 3 (dose #2) and Week 4 (dose #3) should be administered +/- 1 day from when they are scheduled to be administered. If the dose on Week 3 (dose #2) is missed, the dose due on Week 4 (dose #3) should be adjusted to 7 days after dose #2 was given.

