Visit Window Days (d)			± 1d	± 1d	± 3d	± 3d	± 3d	± 3d	± 3d	± 3d	± 3d	
Post vaccine Serum HI titers					X ³							
Administration of study drug			X	X	X	Х	Х	Х	X	Х	X	
Drug Accountability	S				S				S		S	
Adverse Events / Serious Adverse Events	Х	Х	Х	Х	Х	Х	Х	Х	Х	Х	Х	Х
Subject disposition	Х				Х						Х	
Remote Contact		X ⁴	S ⁵	S ⁵		S ⁵	S ⁵	S ⁵		S ⁵	S ⁵	

X = assessment to be recorded in the clinical database or received electronically from a vendor

S = assessment to be recorded in the source documentation only

¹ Participants with lab results within the past 6 months prior to screening will not require labs drawn at screening visit. Local labs should be documented in the source. Participants without lab results from the past 6 months prior to screening will require central labs drawn at the screening visit to be entered into the clinical database.

² Participants will use the pharmacy card to cover the cost of the influenza vaccine. Participants administered the vaccine from investigator site supply will not receive a pharmacy card. All participants should receive the vaccine within 9 calendar days after the Screening Visit, before the Week 0 visit occurs.

³ Post vaccine titer to be drawn before administration of ofatumumab.

⁴ Remote contact to perform a Vaccine Status Check-in by site staff to confirm participant has received the influenza vaccine and to collect any AEs/SAEs.

⁵ Remote contact with participants by site staff. The contact should query about any new AEs or SAEs, changes in con meds and compliance with current treatment. Method of contact can be via telephone, email or text message depending on the preference of each participant.

 Table 8-2
 Assessment schedule for participants (cohort 2)

Period	Screening		Investiga	ational Pe	riod		Unscheduled					
Visit Name	Visit 1 Screening	Visit 2 (vaccine status check- in)	Visit 3 (home visit)	Visit 4 (home visit)	Visit 5 EOS1	Visit 6 (home visit)	Visit 7 (home visit)	Visit 8	Visit 9 (home visit)	Visit 10 (home visit)	Visit 11 EOS2	Unscheduled
Day/Week/Month	Week -1	Week 0	Week 1	Week 2	Week 4	Week 8	Week 12	Week 16	Week 20	Week 24	Week 28	
Visit Window Days (d)			± 3d	± 3d	± 3d	± 3d	± 3d	± 3d	± 3d	± 3d	± 3d	
Obtain informed consent	Х											
Inclusion/exclusion criteria	Х											
Demography	Х											
Relevant medical history/current medical history	Х											
Prior/Concomitant Medications	Х		Х	Х	Х	Х	Х	Х	Х	Х	Х	Х
MS Relapse	Х		Х	Х	Х	Х	Х	Х	Х	Х	Х	Х
Local Serum Pregnancy Test	S											

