1.1 Study design

This is a three-cohort, multicenter prospective study in up to 66 participants with relapsing multiple sclerosis (RMS).

Cohorts 1 and 2 will include up to 44 participants who will either begin treatment with ofatumumab (Cohort 1) or who are already treated with commercial ofatumumab (Cohort 2). Participants in **Cohort 1** will receive the inactivated influenza vaccine two weeks prior to starting treatment with ofatumumab, while participants in **Cohort 2** will receive the inactivated influenza vaccine after at least 4 weeks of commercial ofatumumab treatment.

Cohort 3 will include the remaining 22 participants who are already treated with commercial injectable disease modifying therapy (iDMT) and who will receive the inactivated influenza vaccine after at least 4 weeks of commercial iDMT treatment.

The study consists of three periods:

- Screening Period (1 week);
- Investigational Period (4 weeks);
- Optional, 6-month open-label Extension Period

Screening Period

Participants will enter a Screening Period of up to 1 week to assess eligibility requirements. Participants in Cohort 1 without Hepatitis B virus (HBV) and serum immunoglobulin results within the past 6 months prior to screening will require central labs drawn. Participants with Hepatitis B virus (HBV) and serum immunoglobulin results within the past 6 months prior to screening will not require the labs to be drawn.

Investigational Period

All participants will receive the inactivated influenza vaccine before or during the Week 0 visit, but within 9 calendar days after their screening visit.

- Participants in **Cohort 1**: Loading doses of ofatumumab will be administered at Week 2, 3 and 4.
- Participants in Cohort 2 will continue taking their prescribed of atumumab as per their dosing schedule throughout the investigational period.
- Participants in **Cohort 3** will continue administration of their prescribed iDMT as per their dosing schedule throughout the investigational period.

Optional, 6-month open-label Extension Period

- Participants in **Cohort 1** will administer their first dose of ofatumumab in the open-label Extension Period at Week 6. Thereinafter, they will continue monthly dosing until the final dose at Week 26. Novartis will supply ofatumumab to participants in Cohort 1 for the Extension Period.

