1.2 Study objectives and endpoints

Study objectives and associated endpoints are shown in Table 1-1.

Table 1-1 Study objectives and endpoints

Objective(s) Endpoint(s) Primary objectives(s) Endpoint(s) for primary objective(s) To characterize those achieving Achieving seroprotection as defined by a seroprotection after receiving the 2020post-vaccination antibody titer ≥40 at 2021 seasonal quadrivalent influenza Week 4 (yes/no) vaccine in participants treated with ofatumumab 20 mg sc once every 4 weeks Secondary objective(s) Endpoint(s) for secondary objective(s) To characterize those achieving Achieving seroconversion at Week 4 as seroconversion after receiving the 2020defined by either: 2021 seasonal quadrivalent influenza a. a ≥4-fold increase in HI titers vaccine in participants treated with after vaccination (in participants ofatumumab 20 mg sc once every 4 with pre-vaccination HI titers weeks ≥10) or Safety

Objective(s)	Endpoint(s)
	b. post-vaccination HI titers ≥40 (in participants with pre-vaccination HI titers <10) (yes/no)
	 Change in HI titers
	 AEs, SAEs, AEs leading to discontinuation

2 Statistical methods

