2.1.1 General definitions

Treatment of interest

The investigational treatment or treatment of interest will refer to a once-off administration of the 2020-2021 quadrivalent inactivated influenza vaccine (QIV) via 0.5-mL single-dose prefilled syringe to participants in all three cohorts.

Additional treatment

- Ofatumumab provided by Novartis in an auto-injector containing 20 mg sc ofatumumab (20 mg/0.4ml) for subcutaneous administration to participants in Cohort 1 in the Investigational and optional Extension Periods and to participants in Cohort 2 entering the optional open-label extension period as per the assessment schedule.
- Ofatumumab as commercially prescribed in the course of medical practice for participants in **Cohort 2** for the Investigational Period.
- Any MS iDMT as commercially prescribed in the course of medical practice for participants in **Cohort 3**.

Study day

The day of Week 0 visit is defined as Study Day 1 or Day 1. All other study days will be labeled relative to Day 1.

For event dates **on or after Day 1**, study day for a particular event date is calculated as:

(Date of event - date Week 0 visit) + 1

I.e. Day 2, Day 3, etc., will be one day, two days, etc., after Day 1, respectively.

For dates **before Day 1**, study day for an event date is calculated as:

(Date of event – date Week 0 visit)

Duration of an event will be calculated as (event end date – event start date + 1).

The descriptor "Day 0" will not be used.

Screening, baseline and post-baseline definitions

Screening refers to any procedures (e.g., checking inclusion and exclusion criteria) performed prior to vaccination. Per protocol, participant informed consent must be obtained prior to performing any study related activity. The date of signing of informed consent is the start date of the screening period. Any assessment obtained during the screening period will be labelled screening assessment.

Baseline is the last assessment (including unscheduled visits) obtained before the date of vaccination. No visit windows will be needed for the identification of baseline assessment. All assessments obtained after the date of vaccination are considered as **post-baseline** unless otherwise specified.

Nominal visits

Nominal visits are defined as all scheduled visits as per the clinical study protocol including the EOS visits. The definition of nominal visit excludes unscheduled visits.

Change from baseline

Change from baseline will be calculated as:

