2.2 Analysis sets

Safety set

The Safety Set (SAF) comprises all participants who have received the 2020-2021 inactivated influenza vaccine.

Unless stated otherwise, the SAF will be used for all summary tables and listings.

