2.8 Safety analyses

2.8.1 Adverse events (AEs)

An adverse event (AE) is any untoward medical occurrence (i.e., any unfavorable and unintended sign [including abnormal laboratory findings], symptom or disease) in a participant or clinical investigation of a participant after providing written informed consent for participation in the study. That means that a participant can report AEs before having started study medication. For reporting purposes, the main focus will be on any adverse event which started on or after the Week 0 visit.

The number (and percentage) of participants with AEs will be summarized by cohort in the following ways:

- by primary SOC and PT
- by primary SOC, PT and maximum severity
- by Standardized MedDRA Query (SMQ) and PT

Separate summaries will be provided for:

- serious adverse events (SAEs)
- AEs leading study discontinuation

Separate summaries will be presented for data collected during the Extension Period.

The MedDRA version used for reporting the study will be described in a footnote. If a particular Missing CTCAE grade will not be imputed. If a participant reported more than one AE with the same PT, the AE with the greatest severity will be presented. A participant with multiple AEs within a primary SOC is only counted once towards the total of the primary SOC.

All AEs will be listed by cohort.

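### The SAP focuses AE reporting on onset from the Week 0 visit although vaccination comes first, leaving unclear whether the first post-vaccine days enter the by-cohort AE summaries

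*SAP*

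**What the plan says.** **AE reporting.** SAP 2.8.1 defines an AE from informed consent onward and notes that AEs can precede study medication. It then states: "For reporting purposes, the main focus will be on any adverse event which started on or after the Week 0 visit". The by-cohort summaries that follow carry no onset rule of their own. Every AE also goes into a listing. AEs are a stated endpoint in SAP Table 1-1: "AEs, SAEs, AEs leading to discontinuation".

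**Vaccination timing.** Protocol section 3 (Investigational Period): "All participants should receive an inactivated influenza vaccine within 9 calendar days after the Screening Visit, before the Week 0 Visit occurs". SAP 1.1: "All participants will receive the inactivated influenza vaccine before or during the Week 0 visit", also within 9 days of screening. Protocol section 8 makes Week 0 a remote check-in, and footnote 4 to Table 8-1 gives its purpose: "to confirm participant has received the influenza vaccine and to collect any AEs/SAEs".

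**Role of the vaccine in the SAP.** SAP 2.1.1: "The investigational treatment or treatment of interest will refer to a once-off administration" of the influenza vaccine. SAP 2.2: the Safety Set "comprises all participants who have received the 2020-2021 inactivated influenza vaccine". SAP 2.1.1 also takes baseline before the vaccination date and counts assessments after it as post-baseline.

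**Reference dates.** SAP 2.1.1 sets Day 1 as the Week 0 visit, while the multiple-assessments rule in SAP 2.4.1.1 gives the same label to the vaccination date. SAP 5.1.2 imputes partial AE start dates from a treatment start date (TRTSTD) that the SAP text does not define. Protocol 12.5.2 counts events from the first dose of study medication, and protocol 12.1 defines the Safety Set by study drug.

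**The concern.** Acute reactions to a vaccine are of most interest in the days just after it is given. The SAP treats the vaccine as the intervention everywhere except in the sentence that directs AE reporting, which starts from a later administrative contact. The Week 0 contact collects AEs, so the data exist. But an event that began after vaccination and before that contact lies outside the stated focus.

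At stake is whether the number and percentage of participants with AEs, by cohort, include those first days. As written, that depends on how the focus sentence is read, on which date is taken as Day 1, and on each participant's interval between vaccination and Week 0. Two competent programmers could produce different AE tables from the same data.

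**Working it through.** The plan gives no figure to reproduce here, so the check applies the SAP's own date rules to the vaccination dates that the documents allow.

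**1. Onset days before Week 0.** Inputs: screening at Week -1 (protocol Tables 8-1 to 8-3), so Week 0 is nominally 7 days after screening; vaccination timing as quoted above; and the study-day formula in SAP 2.1.1 (event date minus Week 0 date if earlier than Week 0, plus 1 if on or after it). Let s = days from screening to vaccination and g = 7 − s. The days from vaccination to the day before Week 0 are Study Days −g to −1, which is g days.

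| Vaccination | g | Study day of vaccination | Onset days before Week 0 |
|---|---|---|---|
| Screening + 0 | 7 − 0 = 7 | −7 | 7 |
| Screening + 3 | 7 − 3 = 4 | −4 | 4 |
| Screening + 6 | 7 − 6 = 1 | −1 | 1 |
| Week 0 day (SAP 1.1 only) | 7 − 7 = 0 | 1 | 0 |

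The nominal range is thus 0 to 7 days. It is not a bound. Vaccination up to 9 days after screening, and still before Week 0, means that Week 0 can fall on screening + 10 or later. A participant vaccinated on the screening day with Week 0 at screening + 10 has g = 10. The general ±3-day window in protocol section 8 gives the same value (7 + 3 = 10) if it applies to Week 0, whose window cell is empty in the tables.

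**2. Effect of the undefined TRTSTD.** Take an ongoing AE with only month and year known, in the same month as the reference date. SAP 5.1.2 imputes its onset as the later of the first of the month and the reference date plus 1 day. Suppose vaccination is on Study Day −4 and both dates fall in that month.

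- TRTSTD = vaccination: onset is imputed to Study Day −3, outside the stated focus.
- TRTSTD = Week 0 visit: onset is imputed to Study Day 2, inside it.

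The same record moves in or out according to a date the SAP leaves open. The protocol's first dose of study medication is a third candidate; in Cohort 1 it could be read as ofatumumab at Week 2.

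**3. Separate point: the Week 4 titer window.** By the SAP formula, 28 days after Week 0 is Study Day 28 + 1 = 29, whereas SAP Tables 2-1 to 2-3 put Week 4 at Day 28. With ±3 days, compliant samples fall on Days 26 to 32, which is 7 days.

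| Cohort | Tabulated Week 4 window | Compliant days inside |
|---|---|---|
| 1 | 25 to 35 | 7 of 7 |
| 2 | 22 to 42 | 7 of 7 |
| 3 | 25 to 31 | 6 of 7 (Day 32 is outside) |

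SAP 2.4.1.1 says that these windows serve measurements taken at every visit and that windows are combined for parameters measured less often, such as titers. Combining would not appear to move the upper edge of the last window, so Day 32 remains unsettled.

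**The case against.** The strongest reply is that the focus sentence expresses emphasis. SAP 2.8.1 defines AEs from consent, and the summaries are described without an onset filter, so a literal reader could include every AE, early reactions among them. This stands. A reader might infer that the SAP plans to omit vaccine reactions, and the text does not support that. It supports only that their inclusion is undecided.

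Second, Week 0 may have been meant as a stand-in for the vaccination date. Protocol 6.7.2 describes Week 2 in Cohort 1 as "2 weeks after receiving the influenza vaccine", SAP 1.1 allows vaccination at the visit, and the SAP was written against protocol version 00 rather than the amended version 03. Gaps may therefore be short in practice. But the 6.7.2 wording covers Cohort 1 only, and protocol 6.1.2 says at least two weeks for that cohort. The stand-in fails whenever vaccination comes earlier, which is what the current protocol requires.

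Third, the consequence is limited: there is no hypothesis test, at most 66 participants are enrolled, AEs are descriptive, and no AE data are lost. This also stands. Still, a listing does not supply the by-cohort counts and percentages that 2.8.1 promises.

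On the titer point, a reader might infer that a Day 32 sample in Cohort 3 would be treated as missing and scored as a non-response. The documents do not show this: SAP 2.4.1.1 intends all visits to be mapped to a window, and Table 2-3 is not stated to be the titer window.

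**Conclusion.** The point holds as an anchor that does not fit the SAP's own definition of treatment. Reactions starting between vaccination and Week 0 may be left out of the by-cohort AE summaries, and the wording does not settle it.

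The size is 0 to 7 onset days per participant, assuming Week 0 is 7 days after screening, and more if Week 0 is later. The days concerned are always the first ones after the vaccine. A reader might want a proportion of AEs lost, but the documents give neither the distribution of the gap nor AE onset times, so none can be stated.

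The double use of Day 1, the undefined TRTSTD and the third anchor in protocol 12.5.2 are plain on the text. The seroprotection result does not depend on the AE point. The Cohort 3 window is a minor separate matter affecting one compliant day in seven.

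**What to change.** In the SAP:

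- State in 2.8.1 that the by-cohort AE summaries include all AEs starting on or after the vaccination date, in every cohort.
- Use the vaccination date as the single safety reference for baseline, AE onset and partial-date imputation, and define TRTSTD as that date.
- Reserve Day 1 for the Week 0 visit schedule and remove that label from the vaccination date in 2.4.1.1.
- Separately, state the Cohort 3 Week 4 titer window explicitly so that it covers Day 32.

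Across the two documents, reconcile this with the Safety Set and treatment-emergent wording in protocol 12.1 and 12.5.2, and reconcile the two statements of when vaccination occurs relative to Week 0.

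The SAP changes need wording and programming only, because its baseline rule already requires the vaccination date. Aligning the protocol sections is additional work. The downsides are slightly higher AE counts and the need for a rule for AEs on the vaccination day with no recorded time.

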12.5.2 Safety endpoints

For all safety analyses, the safety set will be used. All listings and tables will be presented by treatment arm.

In particular, summary tables for adverse events (AEs) will summarize only on-treatment events, which started or worsened during the on-treatment period (treatment-emergent AEs).

Adverse events

All information obtained on adverse events will be displayed by treatment group and participant.

The number (and percentage) of participants with treatment emergent adverse events (events started after the first dose of study medication or events present prior to start of double-blind treatment but increased in severity based on preferred term) will be summarized in the following ways:

- by treatment, primary system organ class and preferred term.
- by treatment, primary system organ class, preferred term and maximum severity.
- by treatment, Standardized MedDRA Query (SMQ) and preferred term.

Separate summaries will be provided for study medication related adverse events, death, serious adverse events, other significant adverse events leading to discontinuation, and adverse events leading to dose adjustment.

In addition, a separate listing of death including on treatment and post treatment deaths will be provided.

Clinical laboratory evaluations

All laboratory data will be listed by treatment arm, participant, and visit/time and if normal ranges are available abnormalities will be flagged. Summary statistics will be provided by treatment arm and overall. Shift tables using the low/normal/high/ (low and high) classification will be used to compare baseline to the worst on-treatment value.

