2.14 Interim analysis

For the purpose of earlier dissemination of results, an interim analysis will be performed after:

- all enrolled participants have completed the Investigational Period or discontinued the Investigational Period prematurely OR
- On/around March 29, 2021, whichever comes first.

Since there will be no hypothesis testing involved, statistical adjustment for the interim analysis will not be made at the stage of final analyses.

3 Sample size calculation

Sample size calculations were based on the proportion of participants who responded to influenza vaccination.

The sample size of 20 participants per arm is selected based on budget and need for early availability of results. The sample size of 20 subjects will provide estimates with margin of error (half-width of a 95% confidence interval) of 20.1%, 19%, and 17.5% corresponding to response rates of 70%, 75%, and 80%, respectively. Adjusting for 10% drop-out, 22 subjects will be enrolled in each arm.

4 Change to protocol specified analyses

There are no changes to protocol specified analyses.

5 Appendix

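### SAP 2.8.1 selects adverse events by onset from Week 0, omits the protocol's worsening limb, and pools Cohort 1's days before and after the first ofatumumab dose

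*SAP*

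**What the plan says.** Protocol 12.5.2 states that the adverse event tables will "summarize only on-treatment events, which started or worsened during the on-treatment period (treatment-emergent AEs". Its definition has two limbs. The first is onset: "events started after the first dose of study medication". The second is worsening: "events present prior to start of double-blind treatment but increased in severity based on preferred term".

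SAP 2.8.1 gives a single selection statement: "For reporting purposes, the main focus will be on any adverse event which started on or after the Week 0 visit". It then specifies tables by cohort (system organ class and preferred term, the same with maximum severity, and Standardized MedDRA Query), separate summaries for the Extension Period, and a listing of all adverse events. Treatment-emergent adverse events appear in the SAP's abbreviation list, but 2.8.1 neither uses nor defines the term.

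SAP section 4 states: "There are no changes to protocol specified analyses". SAP section 1 says that the plan implements protocol version 00 of 10 November 2020; the protocol supplied is amended version 03.

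On timing, SAP 1.1 says for Cohort 1: "Loading doses of ofatumumab will be administered at Week 2, 3 and 4". SAP 2.1.1 names the influenza vaccine as the treatment of interest and classes ofatumumab as additional treatment.

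**The concern.** Safety is listed under the secondary objectives in both documents, and the by-cohort adverse event tables are its main output. The two documents would build those tables by different rules.

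Under the protocol, an event that began before treatment and then rose in grade belongs in the tables. Under the SAP's only stated criterion it does not qualify by its original start date. The table most exposed is the one by maximum severity, where a worsened grade is the information of interest.

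The reference date differs too: the first dose of study medication in the protocol, the Week 0 visit in the SAP. In Cohort 1 ofatumumab starts two weeks after Week 0. A single Investigational Period column therefore combines time after vaccination only with time after vaccination plus loading doses. A reader who takes that column as describing early ofatumumab treatment would be misled about what it covers.

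**Working it through.** The selection rule calls for a comparison of texts. The plan states no figure for it that could be reproduced.

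1. **Worsening limb.** Protocol 12.5.2 has it, in both its general statement and its definition. SAP 2.8.1 does not. For concomitant medication, by contrast, SAP 2.4.2 explicitly keeps items that began before Week 0 and continued. There is no matching provision for adverse events.

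2. **Reference date.** The protocol anchors onset on the first dose of study medication, and its worsening limb on the start of double-blind treatment, although the study is open-label (protocol 6.4). SAP 2.8.1 anchors on Week 0. The SAP's own date imputation for adverse events (5.1.2) uses a treatment start date, so two anchors operate within one analysis. The vaccine is given before Week 0 according to the protocol, and before or during it according to SAP 1.1. A new event between vaccination and Week 0 therefore also falls outside the SAP's stated focus.

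3. **Does the SAP exclude worsened events?** Its sentence describes a main focus. The sentence that sets up the tables speaks of participants with adverse events and repeats no onset filter. Exclusion is the likely reading, but it is not stated. Two programmers could build different tables from this text.

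4. **Which events could be affected?** Adverse events exist only from consent (protocol 10.1.1; SAP 2.8.1), and conditions present at consent are recorded as medical history (protocol 10.1.1). The original onset must therefore lie between consent and Week 0. Screening lasts up to 1 week, and vaccination is due within 9 calendar days after the Screening Visit and before Week 0, so this interval is about a week. The event must then also worsen.

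5. **Weight of one participant.** With 22 per cohort, 1/22 = 0.045, or 4.5 percentage points. The documents give no adverse event rates, so the expected number of such participants cannot be calculated.

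6. **Cohort 1 exposure mix.** Ofatumumab starts at Week 2 and the Investigational Period ends at Week 4: 2 × 7 = 14 days of 4 × 7 = 28, and 14/28 = 50%. SAP Table 2-1 labels Week 0 as day 1 and Week 2 as day 14. Counted strictly, that leaves 13 days before the first dose, and 13/28 = 46%. Either way, about half the period precedes ofatumumab.

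7. **Declared changes.** SAP section 4 declares none. Against version 03, points 1 and 2 are undeclared differences. SAP 2.8.1 also lacks the protocol's separate summaries of events related to study medication and events leading to dose adjustment, which supports the view that it does not carry out 12.5.2 as now written.

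**The case against.** The strongest defence is that little is lost. The SAP sets a focus, not a filter, and every adverse event is listed. The interval in which an affected event can begin is about a week. If sites enter a worsening as a new record, it has its own start date, meets the Week 0 criterion, and is carried at its highest grade under the SAP's rule for repeated preferred terms. The study is descriptive, with no hypothesis testing. The defence adds that the vaccine is the SAP's treatment of interest, that the protocol asks for tables by treatment arm, and that neither document calls for Cohort 1 columns before and after ofatumumab.

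Most of this stands as a limit on size. It does not settle the rule: neither document says how a worsening is recorded, protocol 10.1.1 asks only for a grade and dates per event, and a listing does not replace a maximum-severity table. The Cohort 1 split is indeed an addition to the protocol, proposed for interpretation.

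A reader might infer that Cohorts 2 and 3 lose more events than Cohort 1 because they were already on their drug. The documents do not support this. A reaction that predates consent is medical history, and its later worsening could be entered as a new event. That new starters show new ofatumumab reactions follows from the design and would remain under either rule.

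**Conclusion.** The mismatch is real against protocol version 03. SAP 2.8.1 omits the worsening limb and substitutes Week 0 for the protocol's anchor, and SAP section 4 lists neither difference. In Cohort 1, about half of the Investigational Period (14 of 28 days) precedes ofatumumab and is tabulated with the loading-dose days.

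Two stronger conclusions go beyond the text. A reader might infer that worsened events are certain to be dropped from the tables. The wording is ambiguous and all events are listed, so the supportable statement is that they may be left out. A reader might also infer that section 4 was false when written. It relates to version 00, which is not supplied, so that cannot be checked.

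The number of affected participants is unknown and probably small, at 4.5 points of 22 for each. This rests on full enrolment of 22 per cohort and on worsening not being entered as a new record; if it is, the Week 0 rule already captures it.

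**What to change.** In SAP 2.8.1:

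- Define a treatment-emergent adverse event as one that starts after a named reference date, or is already present and increases in severity under the same preferred term after it. The vaccination date is the natural choice, since the vaccine is the SAP's treatment of interest.
- Apply that definition to the system organ class and preferred term, maximum-severity and SMQ tables.
- State that a worsening is recorded as a new adverse event record with its own start date and grade. Without this, the documents do not show that the rule can be derived.
- For Cohort 1, show Investigational Period events before and after the first ofatumumab dose, plus the total. A participant may count in both columns, so a footnote should say that they do not add up.

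In protocol 12.5.2, replace the reference to double-blind treatment with the same reference date. In SAP section 4, list any difference from the current protocol that remains.

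The cost is wording, a recording instruction and slightly more tabulation. Adverse event percentages may become slightly higher, because worsened events and events between vaccination and Week 0 would now clearly count.
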